8.6. Other Clinical Parameters

8.6.1. Nerve Conduction

All nerve conduction data will be analyzed directly from adjudicated datasets provided by the Central Reading site at the Laboratory for Behavioral Neurophysiology, Albert Einstein College of Medicine in Bronx, New York.

All available data will be summarized descriptively for each parameter (sural nerve amplitude and conduction velocity, peroneal motor nerve amplitude and conduction velocity) by treatment group and scheduled visit based on the actual treatment.

A categorical Repeated Measures Model will be used for comparing the percentage of subjects with a \geq 7% and \geq 12% change in Nerve Conduction Velocity for both the peroneal nerve and the sural nerve at 9 months (responder rate) between the two study treatment groups. The model will include treatment, visit, treatment-by-visit interaction, baseline use of gabapentin and/or pregabalin, and baseline average 24-hour pain scores as covariate with an unstructured variance-covariance matrix. The point estimates for the least-squares mean of the treatment difference (VM202 – Placebo) at 9 months and the corresponding 95% confidence interval and p-value will be summarized.

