3.4.8. DAY -7 (-7 DAYS)

• Daily Pain and Sleep Interference Diary

DAY 0-1^{ST} INJECTIONS 3.4.9.

PRE-INJECTION (WITHIN 4 HRS PRIOR TO INJECTIONS)

- Concomitant Medications
- Changes in medical history
- Vital Signs
- VAS
- Brief Pain Inventory for Diabetic Neuropathy (BPI-DPN)
- Semmes-Weinstein Monofilament Testing
- Nerve Conduction (testing may be performed anytime between randomization and/ or on Day 0)
- Serum Chemistry and Hematology
- HbA1c
- Serum HGF
- Copies of VM202 in whole blood

3.4.9.2. 1ST DOSE OF VM202 OR PLACEBO

Sixteen (16) IM injections of randomly assigned study medication in each calf for a total of 32 injections will be administered.

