3.4.17. DAY 180 (6 MONTHS) \pm 7 DAYS

- Daily Pain and Sleep Interference Diary to be completed within 14 days prior to the visit
- Retinal Fundoscopy (testing may be performed anytime within the visit window)
- Concomitant Medications
- Vital Signs
- VAS
- MNSI
- Semmes-Weinstein monofilament testing
- BPI-DPN
- PGIC
- Nerve Conduction (testing may be performed anytime within the visit window)
- Serum Chemistry and Hematology
- HbA1c
- Serum HGF
- Copies of VM202 in whole blood
- Tylenol Usage
- Adverse event assessment

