6. STATISTICAL CONSIDERATIONS

Detailed statistical methods are described in the Statistical Analysis Plan (SAP).

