Appendix 13. Nerve Conduction Testing (at select sites only)

NERVE CONDUCTION⁴ - GENERAL INSTRUCTIONS

Overview: These studies will examine nerve conduction velocity (NCV) and the response amplitude for a distal sensory nerve (i.e., sural nerve) and for a distal motor nerve (i.e., peroneal nerve). These measures will be determined using standard surface electrophysiologic procedures.5

The key analysis will be a comparison of mean NCV measures at baseline, and Day 180:

- NCV will be measured in m/sec to the nearest 0.1 m/sec
- Sensory amplitude will be measured in μV to the nearest 0.1 μV
- Motor amplitude in mV to the nearest 0.1 mV.

Recording procedures, distances, electrode placements, limb temperature, instrument calibration, units of measurement and waveform display and will be standardized across sites. All electrophysiologic procedures will be reviewed by a Central Reading site at the Laboratory for Behavioral Neurophysiology – Albert Einstein College of Medicine in NY.

Skin Preparation

The skin where recording, stimulating, and ground electrodes are placed will be cleaned and lightly abraded at each stimulation and recording site.

Temperature Probe

Skin temperature will be measured at a mid-calf site in each patient at each recording session. If necessary, the skin will be gradually warmed using a Hydroculator or warming pads.

Equipment

The equipment used for electrophysiology at each site will need to meet the following criteria: calibration, capacity for data averaging, capacity for appropriate data printing and display with units of measurement. Units that measure motor NCV from a site off the muscle will not be accepted.

Protocol VMDN-003/H Helixmith Co., Ltd CONFIDENTIAL

⁴ Manual of Nerve Conduction Studies – Second Edition. Ralph M. Buschbacher, Nathan D. Prahlow

⁵ Electrodiagnosis in Diseases of the Nerves and Muscle: Principles and Practice - J. Kumura, 1981

SURAL NERVE SENSORY NERVE CONDUCTION STUDY

Position:

This study is performed in the side-lying position.

[figure not shown]
Recording Electrodes

Commercially available disposable electrodes.

- Active electrode (A): Placement immediately behind the lateral malleolus. The electrode should be placed over the sural nerve on a line that goes from the triceps sural tendon to the prominence of the lateral malleolus perpendicular to the sural nerve.

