8.4.7. Exploratory Efficacy Endpoints

Each exploratory efficacy endpoint (described in Section 4.3, except for PGIC and Semmes-Weinstein monofilament testing) will be analyzed in a manner similar to the corresponding continuous or categorical Repeated Measures Models for the primary analyses described in Section 8.4.2 based on available data of ITT population.

For each such parameter, a repeated measures model analysis will be used accounting for all post-baseline visits where the parameter is collected. The model will include treatment, visit, baseline use of gabapentin and/or pregabalin, and treatment-by-visit interaction as fixed effects and baseline measurement of the parameter as a covariate. An unstructured variance-covariance matrix for the repeated measures model will be used unless convergence problems arise. The point estimate for the least-squares mean of the treatment difference (VM202 – Placebo) and the corresponding two-sided 95% confidence interval at each visit will be summarized.

The 7-category data for PGIC will be combined into 3-category data (1: very much improved, much improved, 0: minimally improved, no change, minimally worse, -1: much worse, very much worse). PGIC will be analyzed at each follow-up visit by Cochran-Mantel-Haenszel (CMH) test to account for the stratification variable and row means scores differ statistic (row variable: treatment group, column variable: 3-category data of PGIC) will be used.

A graph of the cumulative proportion of responders will be generated at each of the 3-, 6-, and 9-month follow-up visits to predict the likelihood of a response for each treatment group and level of the stratification variable (i.e., baseline use of gabapentin and/or pregabalin) over the indicated range of response cutoff-points (20% to 70%) for the reduction from baseline in the average 24-hour pain score.

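### The nerve-conduction responder model adjusts for baseline pain but not baseline nerve conduction velocity, and the mean comparison that Protocol Appendix 13 calls key is tabulated but never estimated

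*SAP*

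**What the plan says.** SAP 8.6.1 plans two things for nerve conduction.

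- **Description.** "All available data will be summarized descriptively for each parameter", by treatment group and scheduled visit, covering amplitude and velocity for the sural and peroneal nerves.
- **A responder model.** A categorical repeated measures model compares the proportions with at least a 7% and at least a 12% "change in Nerve Conduction Velocity for both the peroneal nerve and the sural nerve at 9 months (responder rate"). Its terms are treatment, visit, treatment-by-visit, gabapentin/pregabalin use, and "baseline average 24-hour pain scores as covariate with an unstructured variance-covariance matrix". The treatment difference, 95% CI and p-value are reported at 9 months.

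The covariate phrase is word for word that of the pain-responder model in SAP 8.4.2. For the exploratory endpoints of SAP 4.3 that are modelled this way, SAP 8.4.7 uses the "baseline measurement of the parameter as a covariate". Nerve conduction is listed in SAP 4.5, so that rule does not formally cover it.

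Protocol Appendix 13 states: "The key analysis will be a comparison of mean NCV measures at baseline, and Day 180". Protocol 6 leaves detailed methods to the SAP. Nerve conduction is tested by Day 0 before injection (Protocol 3.4.9), at Day 180 (3.4.17) and at Day 270 (3.4.18). SAP 3 records that the Day 270 test was added in revision E.

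**The concern.** The outcome is percent change from a subject's own baseline NCV. Measurement error and regression to the mean make a low baseline more likely to be followed by a large percent increase, so baseline NCV should predict responder status. Baseline pain has no such built-in link. Using pain alone leaves predictable variation, and any chance imbalance in baseline NCV within a select-site subset, in the comparison. The matching wording suggests the covariate list was carried over from the pain model, though that is inference.

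The only inferential NCV result is dichotomised and reported at 9 months. The mean at Day 180, which Appendix 13 singles out, gets no estimate of difference or precision. At stake are precision and ease of interpretation for this one parameter.

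**Working it through.** **No plan figure to reproduce.** The documents give no NCV sample size, power, mean or SD. The textual point needs no arithmetic. The sizing below rests wholly on assumed values.

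**Comparison of the texts**

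| Item | Pain responders (SAP 8.4.2) | Modelled SAP 4.3 endpoints (SAP 8.4.7) | NCV responders (SAP 8.6.1) |
|---|---|---|---|
| Baseline covariate | Pain | The parameter itself | Pain |
| Own baseline in model | Yes | Yes | No |

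| Item | Protocol Appendix 13 | SAP 8.6.1 |
|---|---|---|
| Quantity | Mean NCV | Means described; responder rate modelled |
| Time | Baseline and Day 180 | Description at each visit; contrast at 9 months |
| Estimate and CI | Not specified | Responder contrast only |

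**Assumptions.** Mean NCV 40 m/s; between-subject CV 10–15%; baseline-to-follow-up correlation ρ 0.7–0.9; mean treatment shift 1–2 m/s; 2:1 allocation; one follow-up visit; pain unrelated to NCV change. Baseline b ~ N(40, sd²) with sd = CV × 40. Follow-up y has mean 40 + ρ(b − 40) + shift (treated only) and variance σ² = sd²(1 − ρ²). Responder: (y − b)/b ≥ 0.07 or 0.12.

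**Step 1. Does baseline NCV predict response?** With sd 6, no treatment effect and ρ 0.7–0.9, the chance of a rise of at least 7% is 29–50% in the lowest baseline quartile and 6–10% in the highest. For 12% it is 12–36% against 1–4%. Baseline NCV is strongly predictive.

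**Step 2. Gain from adding it.** Squared Wald statistic for treatment in a logistic model with b, divided by that without b:

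| Who carries the shift | 7% cut | 12% cut |
|---|---|---|
| All treated subjects | 1.06–1.15 | 1.04–1.16 |
| 30% of treated, same mean shift | 1.01–1.13 | 1.01–1.15 |

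If the unadjusted contrast had 80% power, power becomes Φ(2.80√1.01 − 1.96) = 80.4% to Φ(2.80√1.16 − 1.96) = 85.5%.

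**Step 3. Continuous against dichotomised.** Example: CV 12.5%, ρ 0.8, shift 1.5, all treated shift.

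- sd = 5 and σ² = 25 × 0.36 = 9. The baseline-adjusted continuous contrast has z² per subject = 1.5² / [9 × (3/2 + 3)] = 2.25/40.5 = 0.0556.
- The 7% responder rates are 19.7% and 34.6%. Log odds ratio 0.768; variance 1/(0.667 × 0.346 × 0.654) + 1/(0.333 × 0.197 × 0.803) ≈ 25.6; z² = 0.768²/25.6 = 0.0231.
- Ratio 0.0556/0.0231 = 2.4.

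If 30% of treated subjects each shift by 5 m/s (mean still 1.5), the treated variance rises by 0.3 × 0.7 × 25 = 5.25. The pooled variance is 9 + (2/3) × 5.25 = 12.5, so continuous z² = 2.25/(4.5 × 12.5) = 0.040. The responder z² is 0.0277 and the ratio is 1.4.

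Over the whole grid the 7% ratio is 2.22–4.23 when all treated shift. When 30% shift, its lower end is 1.56 with arm-specific variances and 1.25 with a pooled variance. The working range is therefore about 1.25 to 4.2. If the continuous contrast had 80% power, the 7% responder contrast would have Φ(2.80/√1.25 − 1.96) = 71% down to Φ(2.80/√4.23 − 1.96) = 27%. At the 12% cut the ratio reaches 22, too sensitive to the assumptions to be useful.

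These are single-visit models, not the random-intercept fit shown in SAP 8.4.2. Part of the step 3 ratio overlaps with step 2, because the continuous contrast is baseline-adjusted and the responder contrast is not.

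**The case against.** The case for leaving the plan alone is substantial.

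- **Status.** SAP 4.5 lists nerve conduction among other clinical parameters and SAP 3 calls it a safety assessment. Descriptive handling suits that status. This stands and limits the weight. But SAP 8.6.1 itself plans a CI and p-value, so that model deserves a sensible covariate set. The no-testing rule is in SAP 8.5 and nerve conduction is in 8.6.
- **Appendix 13 is arguably met.** A reader might infer that the SAP drops a required between-arm test at Day 180. The documents do not support that. The appendix sentence does not say whether the comparison is between arms, and asks for no model or CI. The descriptive tables will show mean NCV by arm at baseline and Day 180. What is missing is an estimate of the difference.
- **No bias.** A reader might infer that omitting baseline NCV biases the treatment comparison. Randomisation protects it, and percent change already uses baseline as its reference. The loss is efficiency. In a logit model, adding the covariate also changes the conditional odds ratio being estimated.
- **Already covered.** Day 270 counts by arm follow from SAP 8.6.1 with SAP 8.1, and the NCV sub-population in SAP 6.5 needs only one post-baseline assessment. Nothing further is needed on either. The label of responder points to an increase in NCV; writing the word is optional.
- **Responder analyses are legitimate.** They answer a different question from means and mirror the second primary endpoint. That is why the continuous model is proposed as supportive, not as a replacement.

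**Conclusion.** The point holds as a minor one. The NCV responder model adjusts for baseline pain and omits the same nerve's baseline, which is available and which the SAP uses in the analogous place for its modelled exploratory endpoints. The mean comparison that Appendix 13 calls key is tabulated without an estimated difference or CI.

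The consequence is limited to precision and interpretability. The covariate is worth about 1% to 16% in the squared test statistic, near nil at the low end. The efficiency advantage of a continuous contrast, about 1.25 to 4.2 times at the 7% cut, is larger but depends heavily on the assumed NCV distribution and on how many treated subjects respond. Type I error and the primary and key secondary conclusions are not affected. The text supports neither a claim of a biased analysis nor a claim that a mandated test has been abandoned.

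**What to change.** In SAP 8.6.1:

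1. Add the same nerve's baseline NCV as a covariate in the responder model, and note that the conditional odds ratio being estimated changes with it.
2. Add a repeated-measures model of change in sural and in peroneal NCV with treatment, visit, treatment-by-visit, gabapentin/pregabalin use and that nerve's baseline NCV. Report the treatment difference with 95% CI at Day 180 and Day 270, as supportive beside the responder analysis. Reconcile the Appendix 13 sentence with it, including whether the comparison is between arms.
3. Report the 6-month responder contrast, which the treatment-by-visit model already yields, beside the 9-month one, because Day 270 testing came in only with revision E.

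The cost is SAP wording, one covariate, one added model and a clarifying phrase in Appendix 13. Baseline, Day 180 and Day 270 NCV are already scheduled, so no visit, measurement or alpha is added.

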8.6.2. Total Tylenol (Rescue Medication) Dose

The number and percentage of subjects taking Tylenol during the 9-month follow-up will be calculated by the treatment group. The mean, standard deviation, minimum, maximum, median, and 1st and 3rd quartiles of days to the first start date of the Tylenol will be summarized by the treatment group using observed data; subjects not taking Tylenol will not be included in these descriptive statistics. The total dose of Tylenol of each subject during the 9-month follow-up will be summarized by the treatment group. These analyses will be based on the PP Dosing population.

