3. STUDY DESIGN

This is a phase III, double-blind, randomized, placebo-controlled, multicenter, 9-month study designed to assess the safety and efficacy of bilateral IM injections of VM202 in subjects with painful DPN. Subjects with painful DPN will be screened for study eligibility after giving informed consent.

Patients (from up to 30 sites) who meet the eligibility criteria will be randomized in a 2:1 ratio to one of two treatment groups: VM202 (16 mg) or placebo (VM202 vehicle), respectively. The randomization will be stratified by current use of gabapentin and/or pregabalin so that the enrolled eligible subjects will be randomized using different randomization schedules (with a ratio of 2:1 to VM202 and placebo) based on their use of gabapentin and/or pregabalin. A single treatment with VM202 is delivered as an equally divided dose administered two weeks apart. Subjects will receive VM202 or placebo by intramuscular injections in both legs (in the calf) on Day 0 and Day 14. Subjects will receive a second treatment on Day 90 and Day 104. Injections will be administered as follows:

First Treatment: Days 0, 14

TREATMENT GROUP	DOSE VM202 (n LEG DAY 0	0,	FINAL DOSE VM202 / LEG (mg)	FINAL DOSE VM202 / SUBJECT / TREATMENT (mg)
VM202	4	4	8	16
Placebo	0	0	0	0

0 = injections of VM202 vehicle

Second Treatment: Days 90, 104

TREATMENT	DOSE VM202 (LE		FINAL DOSE VM202 /	FINAL DOSE VM202 / SUBJECT / TREATMENT		
GROUP	DAY 90 DAY 104		LEG (mg)	(mg)		
VM202	4	4	8	16		
Placebo	0	0	0	0		

0 = injections of VM202 vehicle

Patients randomly assigned to the VM202 group will receive the following intramuscular injections in each calf:

- Day 0: 16 injections of 0.5 mL of VM202/calf
- Day 14: 16 injections of 0.5 mL of VM202/calf
- Day 90: 16 injections of 0.5 mL of VM202/calf
- Day 104: 16 injections of 0.5 mL of VM202/calf

Patients randomly assigned to the placebo control group will receive the following intramuscular injections in each calf:

- Day 0: 16 injections of 0.5 mL of VM202 vehicle/calf
- Day 14: 16 injections of 0.5 mL of VM202 vehicle/calf
- Day 90: 16 injections of 0.5 mL of VM202 vehicle/calf
- Day 104: 16 injections of 0.5 mL of VM202 vehicle/calf

The schedule of study visits and the clinical parameters that will be measured at the visits are summarized in Table 1 below.

TABLE 1. SCHEDULE OF EVALUATIONS AND VISITS

		Firs	t Treatmer	nt: D0, D1	.4			Se	cond Treat	tment: D90,	D104	

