6.3 Modified Intent-to-Treat (mITT) Population

The mITT population includes all subjects randomized that meet the following criteria:

- Received at least one dose of study medication.
- Correctly completed the Daily Pain and Sleep Interference Diary at the 3-month follow-up, i.e., by completing a minimum of 5 of 7 days of diary entries within 14 days prior to the Day 90 visit.
- For the mITT population, entries in the Daily Pain and Sleep Interference Diary will be considered fully valid if made anytime during the 24 hour period specified in the date entry.
- Satisfies Inclusion/Exclusion criteria

Subjects will be grouped based on the randomly assigned treatment, not the actual treatment administered. The mITT population will be used in the sensitivity analyses for the primary and secondary efficacy endpoints.

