6.4 Per Protocol (PP) Populations

Three PP populations are defined. All PP population should be absent of any major protocol deviations.

The Per Protocol Medication population is a subset of the mITT and corresponds to the mITT population defined in protocol version H. It includes all mITT subjects who meet the following criterion:

• Have not used the protocol specified prohibited concomitant medications, such as COX-2 inhibitor drug(s) or non-specific COX-1/COX-2 inhibiting drugs which may interfere with VM202 or pain medication usage which may intensify the effect of VM202/placebo on pain, for more than 14 cumulative days during the entire study. The use and effect of protocol specified prohibited concomitant medications will be determined by the Clinical Data Review Committee (CDRC) in a blinded fashion prior to analyses.

The Per Protocol Dosing population is a further subset of the mITT and corresponds to the PP population defined in protocol version H. It includes all mITT subjects who meet the following criterion:

- Subject received all injections based on the randomized treatments.
- Additional criteria, if any, established before unblinding the randomization code by the CDRC that is masked to the treatment information of each study subject.

The Per Protocol Diary population is a subset of the mITT and includes all mITT subjects whose Daily Pain and Sleep Interference Diary at the 3-month follow-up is completed for a minimum of 5 of 7 days within 14 days prior to the Day 90 visit.

All three PP populations will be used in the sensitivity analyses for the primary efficacy endpoints. The PP Medication and PP Dosing populations will also be used in sensitivity analyses of the secondary efficacy endpoints.

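### Rescue acetaminophen is summarised only in the PP Dosing subset while the primary pain result is in ITT, and time to first use leaves out never-users

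*SAP*

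**What the plan says.** SAP 8.6.2 sits under Other Clinical Parameters. It plans, by treatment group, the number and percentage of subjects taking Tylenol, descriptive statistics for days to first use, and total dose. On days to first use it says: "subjects not taking Tylenol will not be included in these descriptive statistics". On dose: "The total dose of Tylenol of each subject during the 9-month follow-up will be summarized by the treatment group". The dose figure is thus one total for the whole follow-up; it is not limited to users and not related to how long each subject was followed. The section ends: "These analyses will be based on the PP Dosing population".

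SAP 6.4 defines that population: "The Per Protocol Dosing population is a further subset of the mITT and corresponds to the PP population defined in protocol version H". Its own criterion is "Subject received all injections based on the randomized treatments", the CDRC may add criteria before unblinding, and a general rule applies: "All PP population should be absent of any major protocol deviations". From mITT (SAP 6.3) it inherits at least one dose, eligibility criteria satisfied, and "Correctly completed the Daily Pain and Sleep Interference Diary at the 3-month follow-up". The injection visits are Days 0 and 14, and then "Subjects will receive a second treatment on Day 90 and Day 104" (SAP 3).

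The primary pain analysis is in ITT (SAP 6.1 and 8.4.2). SAP 6.4 and 8.4.4 also run the pain models in the PP populations as sensitivity analyses.

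On data, protocol 3.4.4 has subjects record the date, time and amount of each use, with tablet counts at visits. The schedule in protocol Appendix 1 and SAP Table 1 ticks Tylenol usage at Early Withdrawal. The list of withdrawal procedures in protocol 3.5.2 does not include it.

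**The concern.** Membership of PP Dosing is settled after randomisation, and partly after the primary endpoint has been measured. Treatment, pain and tolerability can all influence who stays in. A reader who sees a Month 3 pain difference, or none, will want to know how much rescue was taken in each arm by the subjects who produced that result. The plan answers for a narrower group.

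Nothing else specified fills the gap. No pain model includes rescue use. The second set of analyses in SAP 8.4.4 removes scores influenced by prohibited medications, and acetaminophen is permitted. SAP 8.5.6 would cover it only if the CDRC selects it as a medication of interest.

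Two further features limit the tables even within PP Dosing. Days to first use is computed only in those who had the event, so it conditions on the outcome. Total dose mixes differing lengths of follow-up, and mixes the period up to Day 180 with the period after it, when the restriction on starting gabapentin, pregabalin and several other drugs has ended (exclusion criteria 17, 18 and 20).

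**Working it through.** **Who counts where.** The ITT model of SAP 8.4.2, which uses the 3-, 6- and 9-month scores, compared with SAP 8.6.2:

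| Subject | ITT pain model | Rescue summaries |
|---|---|---|
| Valid Month 3 diary, misses Day 90 or Day 104 injections | Month 3 score used | Excluded, including use before Day 90 |
| Valid Month 3 diary, misses Day 14 injections | Month 3 score used | Excluded |
| Valid Month 3 diary, eligibility failure or major deviation | Month 3 score used | Excluded |
| Incomplete Month 3 diary, valid Month 6 or 9 diary | Enters through later visits | Excluded |
| Leaves before Month 3, no follow-up diary | No observed score | Excluded |

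The first four rows are the mismatch. The first arises because the Month 3 diary is completed before the Day 90 visit (protocol 3.4.13), so two of the four injection visits follow it.

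**Does the 10% dropout allowance size this?** SAP 5 needs 286 + 143 = 429 subjects with 3-month data. 429 ÷ 0.90 = 476.7, so 477, which reproduces the plan; 477 − 429 = 48. Those 48 are an allowance for subjects without Month 3 data, mainly the last row. They do not measure the first three rows, for which the documents give no figure.

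**Effect on the share of users (all rates assumed).** Let e be the share of an arm outside PP Dosing, u the user rate inside it and v the user rate outside it. The rate in all randomised subjects is (1 − e)u + ev. Take u = 50% in both arms, so PP Dosing shows no difference.

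- e = 10% on VM202 and 20% on placebo, v = 70%: 0.9 × 50 + 0.1 × 70 = 52% against 0.8 × 50 + 0.2 × 70 = 54%, a gap of 2 points.
- Same e, v = 90%: 54% against 58%, a gap of 4 points.
- e = 10% in both arms with equal v: no gap (52% in each at v = 70%, 54% in each at v = 90%).

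With 318 and 159 randomised, these exclusions would leave about 286 on VM202 (318 × 0.9) and 143 to 127 on placebo (159 × 0.9 to 159 × 0.8).

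**Effect on days to first use (assumed constant hazard, 270 days).** With user probability p, the hazard is λ = −ln(1 − p) ÷ 270. The users-only mean is 1/λ − 270(1 − p)/p, the users-only median is −ln(1 − p/2)/λ, and the mean rescue-free time over 270 days with everyone counted is p/λ.

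| | p = 40% (VM202) | p = 60% (placebo) | Gap, days |
|---|---|---|---|
| 1/λ | 528.6 | 294.7 | |
| Users-only mean | 528.6 − 405 = 123.6 | 294.7 − 180 = 114.7 | 8.9 |
| Users-only median | 118 | 105 | 13 |
| Rescue-free time, all subjects | 0.4 × 528.6 = 211.4 | 0.6 × 294.7 = 176.8 | 34.6 |

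The users-only mean shows 8.9 ÷ 34.6, about a quarter, of the difference.

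**Total dose.** At the same constant daily use r, a PP Dosing subject who leaves just after the fourth injection visit totals about 104r and a completer 270r, a ratio of 2.6 with no difference in use.

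**The case against.** The table is descriptive: no hypothesis, no alpha, and no primary or secondary conclusion depends on it. The percentage of users is reported by arm, so never-users are visible, and the users-only rule is stated openly. This stands, and it limits how much the point matters.

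Four stronger readings are tempting and are not supported.

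- A reader might infer that this table is the plan's check on whether rescue use explains the pain result, or that rescue is the main rival explanation. The SAP says neither. It is simply the only rescue analysis specified.
- A reader might infer that the rescue table has no pain result to sit beside. It has one: the PP Dosing sensitivity analysis (SAP 6.4 and 8.4.4). What is missing is a rescue summary to match the ITT result.
- A reader might take the dropout allowance as a floor, with at least 48 of 477 excluded. It is a planning figure for missing Month 3 data, and most such subjects would have no observed Month 3 score in ITT either.
- A reader might infer a known bias: that the excluded are heavy users, or that users-only timing makes the arm with fewer users look worse. The documents say nothing about rescue use among those excluded. In the illustration the arm with fewer users still looks better, only by less. A reversal would need few but early users, and nothing in the documents suggests that.

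The objection also bears on the remedy. Tylenol is dispensed from Day 0, so the 7 subjects withdrawn untreated (footnote to SAP 6.1) cannot have study rescue data. A treated population therefore fits better than strict ITT. It departs little from it on that account: 7 ÷ 477 = 1.5% of the planned number.

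**Conclusion.** The point holds in a limited form. All planned rescue summaries are confined to a subset selected after randomisation, which can exclude subjects whose Month 3 scores are in the primary result. Time to first use conditions on being a user, and total dose ignores time on study. These follow from the text and need no assumption.

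The size does not follow from the text. The number excluded and the direction of any bias cannot be derived. The shift of 0 to 4 points in users, and the loss of about three quarters of the gap in mean time to first use, rest on assumed rates and show only what is possible. No primary or secondary test changes. The correction is worth making because it is cheap and these are the only rescue summaries specified.

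Separately, SAP 6.4 equates PP Dosing with the protocol version H PP population, but protocol 6.2.4 has no explicit all-injections criterion. The two should be reconciled.

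**What to change.** Amend SAP 8.6.2 before unblinding:

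1. Make the main rescue summary all randomised subjects who received at least one study injection, grouped as randomised so that it can sit beside the ITT pain result. Keep PP Dosing as supportive, beside its own pain sensitivity analysis.
2. Report the percentage of users and average grams per day on study (grams in the period divided by days followed in it) for Day 0 to 90, Day 90 to 180 and Day 180 to 270. The first period then stands alone for the primary endpoint.
3. Give time to first use by Kaplan-Meier, with never-users censored at last contact.
4. Reconcile the withdrawal list in protocol 3.5.2 with the schedule, which includes Tylenol usage at Early Withdrawal.

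The cost is SAP wording and a few extra tables. Dated use and tablet counts are already planned, so no new assessment is needed. The downside is that rescue data may be incomplete for some early withdrawals, particularly at any site that followed the list in 3.5.2; the tables should state how many subjects contribute to each period.
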